- 1) To include the risks associated with male-mediated teratogenicity and to recommend condom use for the duration of drug treatment and for three months post-treatment if the individual engages in sexual intercourse with a woman of child-bearing potential. However, condom usage is not a requirement for entry in the trial (i.e. not an Inclusion Criteria). *Please see protocol section 8.3.1- Risks of pregabalin*
- 2) To include a baseline platelet count so that individuals with a low blood platelet count (less than 100,000/mm³) are excluded from entry in the trial. Additionally, those individuals with a history of thrombocytopenia or a bleeding diathesis are also excluded. These precautions are being taken because in clinical studies, decreases in platelet counts were observed more frequently with pregabalin than with placebo. *Please see protocol sections 5.3- Laboratory Procedures, 6.2- Exclusion Criteria (#3 and #8), 8.3- Risks of pregabalin, 9.2- Screening Visit, and 9.3- Screening /Randomization Visit.*
- 3) To exclude individuals with New York Heart Association Class III or IV congestive heart failure. This precaution is being taken because weight gain and swelling are common side effects associated with pregabalin, and may be a serious problem for people with heart problems. The long-term cardiovascular effects of pregabalin-associated weight gain are unknown. Please see protocol sections 6.2- Exclusion Criteria (#7) and 8.3- Risks of pregabalin.

- 4) To exclude individuals taking thiazolidinedione antidiabetic agents (i.e. rosiglitazone and pioglitazone) because these drugs can cause weight gain and/or fluid retention, possibly exacerbating or leading to heart failure. Please see protocol sections 6.2- Exclusion Criteria (#6) and 8.3- Risks of pregabalin.
- 5) To exclude individuals with a history of alcohol abuse given the potential abuse liability of pregabalin. Pregabalin is classified as a Schedule V Controlled Substance. Please see protocol sections 6.2- Exclusion Criteria (#10) and 8.3- Risks of pregabalin.
- 6) To replace having to send the NIH-CPSI and Symptom Assessment questionnaires (including the GRA question) to the patient prior to the Telephone Contacts in both Phases I and II of this trial. Instead of having the patient complete and send back, the questionnaires will be administered to the patient over the telephone. Please see protocol sections 9.4 Telephone Contacts and 9.7 Phase II Continuation.
- 7) To replace previous SAS references (*Protocol Section 13.0 #35-42*) with one citation for the most recent version of the statistical software package (Version 8.0).

CHRONIC PROSTATITIS COLLABORATIVE RESEARCH NETWORK-2 (CPCRN-2)

RANDOMIZED CLINICAL TRIAL (RCT) #2

A Randomized, Placebo-Controlled Multicenter Clinical Trial to Evaluate the Efficacy and Safety of Pregabalin for the Treatment of Chronic Prostatitis/Chronic Pelvic Pain Syndrome (CP/CPPS)

SUMMARY OF PROTOCOL AMENDMENT #2

The second edition of this protocol is being amended as of the effective date August 16th, 2006. Please refer to the Version 3.0 protocol table of contents for the location of changes listed below.

3.2 Study Design

The following text has been revised:

Each of the eleven (11) sites will randomize approximately 29 participants at a rate of two (2) participants per month. Recruitment will be conducted over a period of fifteen (15) months. A formal pre-planned interim analysis will be conducted when 159 participants have been randomized and have completed the 6 week primary endpoint visit.

Revised text reads:

Recruitment will be conducted over a period of fifteen (15) months, at a rate of approximately two (2) participants per month for each of the ten (10) sites, with the total expected randomized per site of 32 participants. A formal pre-planned interim analysis will be conducted when 106 participants have been randomized and have completed the 6 week primary endpoint visit.

4.0 Study Organizations

University of Sciences Malaysia has been removed as a participating sub-site.
University of Washington/Harborview has been removed as a participating site.

5.3 Laboratory Procedures

Additional text reads:

A platelet count of obtained up to four (4) weeks prior to screening visit #1 will be acceptable as satisfying screening visit requirements.

6.2 Exclusion Criteria

The following exclusion criterion has been revised:

1. Participant has evidence of facultative Gram negative or enterococcus with a value of ≥ 1000 CFU/ml in mid-stream urine (VB2).

Revised, additional text in bold:

1. Participant has **continued** evidence of facultative Gram negative or enterococcus with a value of ≥ 1000 **and** $\leq 100,000$ CFU/ml in mid-stream urine (VB2), **as demonstrated by repeat culture obtained no less than seven (7) days post antibiotic treatment.**

6.3 Deferral Criteria

The following deferral criterion has been revised:

1. Participant has had previous gabapentin (Neurontin®) treatment within the past two (2) weeks.

Revised, additional text in bold:

1. Participant has had previous gabapentin (Neurontin®) or **pregabalin (Lyrica®)** treatment within the past two (2) weeks.

7.2 Phase II Dosing Schedule

Additional text for clarification reads:

As indicated in Section 3.2 Study Design, the transition in dosing from phase I to phase II occurs regardless of phase I treatment assignment or dose, with the study blind intact. Although this could result in a transition from 600 mg/day active treatment to 150 mg/day active treatment for a participant, such a transition is not expected to be of any clinical relevance.

9.2 Screening Visit (Visit #1)

Additional text under *Blood Specimen*:

A documented copy of laboratory results obtained up to four (4) weeks prior to screening visit #1 will be acceptable for these specimens.

9.3 Screening/Randomization Visit (Visit #2)

The following text has been revised:

- *Review VB2 Culture Results.* The research staff will review culture results from the baseline visit to determine participant eligibility. Participants will be excluded from the trial if they have evidence of facultative Gram negative or enterococcus with a value of \geq 1000 CFU/ml.

Revised, additional text in bold:

- *Review VB2 Culture Results.* **The research staff will review culture results from the baseline visit to determine participant eligibility. Participants will be excluded from the trial if they have *continued* evidence of facultative Gram negative or enterococcus with a value of \geq 1000 *and* \leq 100,000 CFU/ml, as demonstrated by repeat culture obtained no less than seven (7) days post antibiotic treatment.**

9.6 Dose Taper Phase

Additional text reads:

Participants who were only able to tolerate the 300mg/day dose will taper down for 4 days at 150mg/day. Participants who were only able to tolerate the 150mg/day do not need to taper down.

12.10 Data Safety Monitoring and Interim Analysis

This section has been revised at the request of the UPPCRN Data and Safety Monitoring Board (DSMB) so that the interim analysis of efficacy and safety occurs earlier in the recruitment period. This is to ensure that sufficient time exists between the results of the interim analysis and the end of recruitment such that decisions regarding early closure or protocol amendments can have an appropriate impact on enrollment. The interim analysis will now take place after approximately one third (n=106) of the participants have been enrolled and followed for six weeks. It is expected that this will occur approximately ten (10) months after the initiation of accrual.

Table of Contents:

1.0	Introduction.....	1
2.0	Study Agent and Rationale for Use in CP/CPPS.....	2
2.1	Pregabalin	2
3.0	Study Design and Objectives.....	3
3.1	Primary Study Objectives.....	3
3.2	Study Design.....	3
4.0	Study Organizations.....	5
5.0	Study Endpoints.....	6
5.1	Primary Endpoint.....	6
5.2	Secondary Endpoints	6
5.3	Laboratory Procedures.....	7
6.0	Study population.....	8
6.1	Inclusion Criteria	8
6.2	Exclusion Criteria	8
6.3	Deferral Criteria.....	9
7.0	Treatment Procedures	10
7.1	Phase I Dosing Schedule.....	10
7.2	Phase II Dosing Schedule.....	11
7.3	Drug Manufacturing and Packaging.....	11
7.3.1	Pregabalin	11
7.3.2	Placebo for Pregabalin	11
7.4	Concomitant Medications.....	11
7.4.1	Drug Interactions:	11
7.4.2	Exclusionary medical condition:.....	12
8.0	Participant Recruitment and Consent.....	13
8.1	Participant recruitment.....	13
8.2	Informed Consent.....	13
8.2.1	HIPAA Authorization.....	13
8.2.2	Patient Confidentiality	13
8.3	Risks and Benefits to Participants.....	13
8.3.1	Risks of pregabalin	14
8.3.2	Risks of placebo.....	15
9.0	Trial Tests and Procedures.....	16
9.1	Procedural Summary.....	16
9.2	Screening Visit (Visit #1).....	16
9.3	Screening/Randomization Visit (Visit #2).....	17
9.4	Telephone contacts.....	18
9.5	Treatment Visit (Visit #5).....	18
9.6	Dose Taper Phase.....	19
9.7	Phase II Study Continuation	19
10.0	Adverse Events and Participant Withdrawals.....	21
10.1	Serious Adverse Events	22
10.2	Reporting Obligations for SAEs and IND Safety Reports.....	22
10.3	Follow-Up of Serious Adverse Events	22

10.4	Unmasking (Unblinding) of Treatment	23
10.5	Participant Withdrawals.....	23
11.0	Administrative Responsibilities.....	24
11.1	General Considerations and the Manual of Operating Procedures (MOP).....	24

1.0 Introduction

Chronic Prostatitis/Chronic Pelvic Pain Syndrome (CP/CPPS) is a chronic pain syndrome of unknown etiology. The current NIH definition of CP/CPPS includes genitourinary pain with or without voiding symptoms in the absence of uropathogenic bacteria, as detected by standard microbiological methods, or another identifiable cause such as malignancy.¹ The accepted research definition is that of chronic pelvic pain for at least 3 of the preceding 6 months in the absence of other identifiable causes. Although the etiology and pathogenesis of the symptoms in CP/CPPS are unknown, one proposed mechanism is that of a neurogenic origin. The defining symptom in participants with CPPS is pain. This indicates some neurologic involvement, either locally or centrally.

This idea is supported by data from the NIH sponsored Chronic Prostatitis Cohort study, in which a history of neurologic disease was almost five times more likely in the cases compared to the controls.² One of the few biomarkers to correlate with the levels of pain in CP/CPPS is nerve growth factor (NGF).³ NGF is a neurotrophin that has been found to have a role in the regulation of nociceptive nerves, and as a mediator and amplifier of neurogenic inflammation. NGF regulates the sensitivity of adult sensory neurons to capsaicin, which excites C-mechano heat receptors.⁴ Data from animal studies also indicates a possible neurogenic mechanism. Experimental evidence for central remodeling is provided by the finding that chemical irritation of the rat prostate and bladder causes c-fos expression at spinal cord levels L6 and S1 along with plasma extravasation in the skin at the identical L6 and S1 dermatomes, underscoring the overlap of afferent nerve fiber distribution.⁵ One of the hallmarks of such remodeling or windup is neurogenic inflammation. In the Wistar rat model of spontaneous prostatitis with age increased nerve fiber density, the sensory neuropeptide calcitonin gene-related peptide and evidence of progressive mast cell degranulation are noted at progressive ages.⁶ One of the products released from activated mast cells is nerve growth factor (NGF).⁷

Given this, one way to treat participants with CP/CPPS would be with medications used to treat neuropathic pain. One such medication is the antiseizure medication gabapentin. In this study, we propose to use pregabalin, developed as a follow-up compound to gabapentin. Pregabalin received FDA approval in late 2004 for treatment of neuropathic pain associated with postherpetic neuralgia and diabetic peripheral neuropathy. One of the advantages of using pregabalin is that its binding affinity to the alpha-2-delta subunit of voltage gated calcium channels is six-fold greater than that of gabapentin.⁸ Therefore, a lower pregabalin dose can be used to achieve efficacy, which will result in fewer side effects for the participant.

2.0 Study Agent and Rationale for Use in CP/CPPS

2.1 Pregabalin

Pregabalin is a new medication which has recently been approved for the treatment of post herpetic neuralgia and diabetic neuropathy. Pregabalin is an antiepileptic medication that also has effects on chronic pain. Although structurally related to GABA, it does not act at GABA receptors and does not act in a physiologically similar way to GABA.⁹ It binds to the alpha-2-delta subunit of voltage gated calcium channels, selectively attenuating depolarization induced calcium influx into neurons via presynaptic channels, and reduces the release of several excitatory neurotransmitters including glutamate, noradrenaline, and substance P.¹⁰⁻¹³

There are three full published studies of pregabalin for neuropathic pain, two of which looked at its effect on post herpetic neuralgia and one on diabetic peripheral neuropathy. All of these studies used pregabalin in a three times per day (tid) dosing. Dworkin et al¹⁴ used dose of 300 mg per day in three divided doses or 600 mg per day in three doses. The decision on which dose to use was made based on creatinine clearance; participants with a clearance of < 60 ml/min received 100 mg po tid; those with a clearance > 60 ml/min received 200 mg po tid. Sabatowski et al⁸ used doses of 150 and 300 mg po in three divided doses in a random fashion. Participants with a creatinine clearance calculated from their serum creatinine of <30 ml/min were excluded from the study. The diabetic neuropathy study¹⁵ compared 300 mg per day as 100 mg po tid vs placebo; no dose escalation was used for this trial. Pregabalin has been used in a twice per day dosing in a study published in abstract only to date.¹⁶ The twice per day study went up to 600 mg per day. Pregabalin is approved for use by the EU for neuropathic pain, including PHN and diabetic neuropathy, at doses of 150-600 mg as either bid or tid dosing. The dose can be titrated up from 150 per day to 300 mg per day after 3-7 days. The dose can then be increased to 600 mg per day if needed after an additional 7 days.¹⁷

The efficacy appears to follow a dose dependent effect.¹⁷ Double blind study completion rates also appear to be dose dependent, reported at 88% and 79% with 150 mg and 300 mg per day of pregabalin vs 75% placebo⁸ and reduced to 65% for the 600 mg dose¹⁴ in the studies on PHN. In the diabetic neuropathy study at dose of 300 mg per day, the completion rate was 86% compared to 89% of placebo participants in this trial.¹⁵ The main side effects seen in clinical studies include dizziness, somnolence, peripheral edema, headache, dry mouth and diarrhea. The side effects of dizziness, somnolence and peripheral edema are also dose related, but with little difference between the 300mg and 600 mg per day in tid dosing.¹⁷

In trials, the analgesic effects of pregabalin are seen in the first week^{8,15} and as early as the second day.¹⁴ The above referenced trials were all for 8 weeks. This included a dose escalation in one trial.¹⁴ This rapid effect onset justifies a proposed trial of six (6) weeks of treatment in order to minimize participant exposure.

[figure not shown]
3.0 Study Design and Objectives

3.1 Primary Study Objectives

1. To compare six (6) weeks of treatment with pregabalin versus placebo in CP/CPPS participants with respect to the primary endpoint in the NIH-CPSI
2. To evaluate the safety and tolerability of six (6) weeks of pregabalin in CP/CPPS participants

3.2 Study Design

A schematic of the design of the proposed two-armed double-blind randomized clinical trial is shown below.

Phase I:

All participants who meet eligibility criteria at baseline screening will be randomized to either pregabalin (utilizing a dose escalation of pregabalin from 150 mg to 300 mg and finally to 600 mg daily) or an identical looking placebo. In the dose escalation, if a participant experiences side effects at a particular dose, he will be allowed to drop back to the maximum tolerated dose. Participants will be advised to take the medication three times per day (tid).

The goal is to randomize a total of 318 participants with an allocation ratio of 2:1, treat and follow them for a total of six (6) weeks. Eligibility for the trial and assessment of treatment efficacy will occur over three (3) visits: a screening visit, a baseline/randomization visit and an endpoint evaluation visit after six (6) weeks. There will also be two (2) phone contacts: at the end of week 2 and week 4 to obtain information on adverse events and symptom scores during the drug titration period.

Recruitment will be conducted over a period of fifteen (15) months, at a rate of approximately two (2) participants per month for each of the ten (10) sites, with the total expected randomized per site of 32 participants. A formal pre-planned interim analysis will be conducted when 106 participants have been randomized and have completed the 6 week primary endpoint visit.

Phase II

We are also proposing an optional open-label phase for this trial. The purpose for this extension is to improve recruitment. Participants who understand that they will be eligible to try a new drug at the end of a masked treatment period during which they have a 33.3% chance of receiving a placebo will be more likely to enter such a trial. At the same time, we will be able to obtain some uncontrolled efficacy and safety data on the use of pregabalin in a

longer treatment period. Participants will have the option to enroll after completion of the initial six (6) weeks of treatment. All participants, regardless of what they were previously on in Phase 1, will be offered active therapy and followed for an additional six (6) weeks. Participants will remain blinded to their initial treatment assignment until the end of the open label phase. Participants are not obligated to participate in the open label extension. Those participants who discontinue study participation will be instructed to begin a one (1) week taper from the study drug, before complete discontinuation.

5.0 Study Endpoints

5.1 Primary Endpoint

The primary endpoint to be used for efficacy evaluation is the response rate, defined as a 6-point decrease from baseline to 6 weeks in the NIH-CPSI Total Score (scale of 0 - 43).¹⁸ The decision to use this 6-point cut-off is based on analysis of the previous CPCRn clinical trial on ciprofloxacin and tamsulosin.¹⁹ The NIH-CPSI total score responsiveness to change, from baseline to 6-weeks, was examined relative to the GRA outcome scale and the two scales were shown to have a high correlation. Among those who reported “moderately improved” or “markedly improved” (n=39) on the GRA, 30 participants reported a ≥ 6 -point decrease. This translates into 77% sensitivity and 71% specificity.

The responder criteria based on a 6-point decrease in the CPSI Total Score will allow detection of clinically detectable improvement in symptoms, as the goal is to identify treatment agents with solid clinical efficacy.

Using a 6-point decrease rather than the mean score change as primary outcome may result in somewhat less statistical power, but it allows study withdrawals to be considered as non-responders for an intent-to-treat analysis. (The dropout rate for the previous CPCRn trial was approximately 10% over 6-12 weeks).

5.2 Secondary Endpoints

A number of secondary outcome measures related to both specific symptoms and overall symptom scores will be used to supplement the analysis based on the primary endpoint. One secondary endpoint will be a participant-reported Global Response Assessment (GRA) of symptom change at twelve (12) weeks relative to baseline or withdrawal; whichever comes first. Additional symptom-related secondary outcome measures include the subscales of the NIH-CPSI (for pain, urinary symptoms, and quality of life), the McGill Pain Questionnaire (a measure of pain intensity), the MOS SF-12 (a measure of health-related quality of life), the Hospital Anxiety and Depression Scale (a measure of depressive symptom severity), and the Sexual Health Inventory for Men (SHIM) (a measure of male sexual function). When combined, the primary and secondary endpoints address all of the recommended core outcome domains for chronic pain clinical trials. Laboratory and procedural measures to be assessed at baseline include urine screening, expressed prostatic secretions (EPS), and blood tests.

Additional details of the proposed secondary endpoints are provided below:

- *Global Response Assessment (GRA)*: The GRA is a single question participant-driven symmetrical outcome scale with seven categories ranging from 1 for “markedly worse” to 4 for “no change” to 7 for “markedly improved”. The GRA has been recommended as the primary outcome measure for interstitial cystitis (IC) trials²⁰ and has been used as the primary outcome measure in two NIDDK sponsored studies in IC. This question will only be asked during follow-up visits.
- *Hospital Anxiety and Depression Scale (HADS)*-This 14-question scale provides scores for the independent measures of anxiety and depression.

- *McGill Pain Questionnaire (MPQ)*: The MPQ will be used because it evaluates the quality of pain as well as the intensity of pain, adding a dimension that the NIH-CPSI does not capture. Total pain scores and both subscores of sensory and affective pain will be evaluated.
- *Medical Outcomes Study Short Form 12 (SF-12)*: Both the Physical Composite Score (PCS) and the Mental Composite Score (MCS) will be evaluated.
- *Pain Medication Questionnaire (PAIN)*: These are individual questions to assess the impact of pain medications on patients enrolling in the trial.
- *Sexual Health Inventory for Men (SHIM)²¹*: This 5-question index is an abbreviated form of the International Index of Erectile Function.²¹ The SHIM includes questions about confidence in the ability to achieve an erection, the frequency with which participants are able to achieve and maintain erection sufficient for penetration, difficulty in completing intercourse, and the frequency with which intercourse is satisfactory. Each question is scored on a scale of 1 to 5, with 5 indicating better function. A score of ≥ 22 is considered normal.
- *Symptom Assessment Form (SYM)*: These are individual questions about pain, urgency and abnormal frequency obtained on 0 – 10 Likert scales.

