12.0 Statistical Considerations

12.1 Summary of Study Design

The proposed study design is a two-arm, double blind, randomized clinical trial (RCT) to evaluate the efficacy and safety of pregabalin, as compared to matching placebo. The primary endpoint on which sample size requirements are based is the comparison of response rates, with responder being defined in terms of a decrease in the NIH-CPSI total score as described in Section 2.6. The proportion of “responders” in each treatment arm will be compared, in an intent-to-treat analysis, to evaluate the overall efficacy of the active therapy as compared to placebo. Approximately 318 eligible participants, 212 in the active treatment arm versus 106 in the placebo arm, will be randomized and followed for a period of six (6) weeks after randomization for the primary, and all secondary endpoints analyses.

An open-label phase for this trial (Phase II) will be offered to all participants after completion of the initial six (6) weeks of treatment, with the exception of those having a Serious Adverse Event while on study treatment in Phase I. Participants on active therapy or placebo will be offered active therapy and followed for an additional six (6) weeks. Participants will remain blinded to their initial treatment assignment until the end of the open label phase. The Phase II study is for the purpose of evaluating long term treatment effect. The GRA, NIH-CPSI will be re-examined again at the end of the Phase II.

An overview of the design considerations and statistical analysis plan, including sample size and power considerations, is provided in the following sections. Additional details will be provided in the study Data Analysis and Monitoring Plan (DAMP), provided prior to study initiation.

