12.4 Intent-to-Treat Analyses and Missing Data

An intent-to-treat analysis, including all randomized participants, will be used for the primary comparison of treatments. All attempts will be made to keep missing data to a minimum. Participants who discontinue treatment during the trial, particularly in the case of an adverse event, will not be considered withdrawals from study unless they withdraw consent for further follow-up. These participants will be encouraged to continue on study in order to provide complete follow-up information. However, it is expected that up to 15% of the randomized participants may withdraw prior to the final assessment of response at six (6)

weeks. These participants will be considered treatment failures and included in the denominator for evaluation of response rates defined for the primary endpoint.

The characteristics at time of randomization for those participants without complete follow-up will be examined; however, there will be limited statistical power to detect any but major differences between these participants and those with complete follow-up. In addition, in order to assess the potential biases introduced by differential withdrawal among treatment arms, a comparison of withdrawal rates and/or time to withdrawal will be included as an ancillary analysis to the primary endpoint comparison.

In general, missing data will not be imputed. The possible exception is validated symptom scales for which methods of imputing missing items have been previously developed. For example, the following procedure will be used to calculate the NIH-CPSI Pain Score in the event there are missing responses. If no more than two binary items are missing from the NIH-CPSI questions 1a-1d, 2a, 2b, and no other pain items are missing, the NIH-CPSI Pain Score will be imputed as follows: $\text{sum of all non-missing items} * 21 / (21 - \# \text{ missing items})$. If only question #3 is missing then the NIH-CPSI pain score will be imputed as follows: $\text{sum of all non-missing items} * (21/16)$. Every effort will be made to use statistical methods that are robust to missingness, and the number of subjects included with each analysis will be given with the results.

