12.8 Secondary Analyses

A number of secondary analyses will be conducted, both to evaluate the secondary symptom-related outcomes and to supplement the primary endpoint comparison. Secondary outcomes are listed in Section 3.3 and include the Global Response Assessment (GRA), subscores of the NIH-CPSI, the Medical Outcomes Study short Form 12 (MOS SF-12), the McGill Pain Questionnaire (MPQ), the Hospital Anxiety and Depression Scale (HADS), the Sexual Health Inventory for Men (SHIM).

For example, one type of response will be based on the participant GRA of change as measured at six (6) weeks or withdrawal, whichever comes first. One method of analysis will be to classify participants who indicate that they are “moderately” or “markedly” improved as intervention responders. The analysis of this binary outcome will be identical to that described for the primary endpoint above. Additional analysis examining the correlation between a 6-point decrease and/or a 25% mean change in the NIH-CPSI could also be conducted, if needed to provide additional measures of responsiveness.

For the various measures evaluated repeatedly over time, changes over time will be compared among treatment groups using methods for longitudinal data analysis.³³ These methods will include random effects regression models for continuous outcomes and GEE methods for categorical and ordinal outcomes such as the GRA.³³ Both within- and between-participant variability in these outcomes will be carefully assessed to provide pilot data for future clinical trials. When applicable, additional analyses of the symptom outcomes may include evaluation of secondary response rates defined by specific changes in symptoms (i.e. 50% drop in symptom score). For measures obtained only at baseline and one follow-up time point, change from baseline will be compared among groups using analysis of variance (ANOVA) and regression methods. Withdrawal rates will be compared between arms using standard methods. Also, modeling the informative of dropout patterns may be conducted to

address whether or not the extent of adherence at 6 weeks is associated with the level of treatment response.

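### Section 5.2 sets the GRA secondary endpoint at 12 weeks, after both arms have been offered open-label pregabalin, while Sections 12.1 and 12.8 analyse it at 6 weeks

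*Combined protocol and SAP*

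**What the plan says.** Section 5.2 introduces the secondary endpoints and gives a time point for one of them: "Global Response Assessment (GRA) of symptom change at twelve (12) weeks relative to baseline or withdrawal; whichever comes first".

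The statistical sections give a different time. Section 12.1 has participants "followed for a period of six (6) weeks after randomization for the primary, and all secondary endpoints analyses". Section 12.8 says that "one type of response will be based on the participant GRA of change as measured at six (6) weeks or withdrawal, whichever comes first". It classes men who report moderate or marked improvement as responders and says this binary outcome is analysed in the same way as the primary endpoint.

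On design, Section 3.2 says of the randomized participants that the goal is to "treat and follow them for a total of six (6) weeks". It then adds an optional open-label phase: "All participants, regardless of what they were previously on in Phase 1, will be offered active therapy". Sections 9.7 and 12.1 exclude men who had a serious adverse event in Phase I. Section 12.9 allows only exploratory analyses of Phase II, because those who enter may not be a random sample of those randomized.

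Appendix A collects the GRA, as part of the symptom assessment form, at both Visit 5 (week 6) and Visit 9 (week 12).

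**The concern.** One endpoint has two pre-specified time points in the current text. The amendment summaries list no change to the GRA timing, so neither time is marked as superseded. The Data Analysis and Monitoring Plan, to which the protocol defers detail, is not among these documents and cannot be assumed to settle the matter.

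The two times do not answer the same question. At week 6 the GRA compares pregabalin with placebo, blinded and as randomized. At week 12 it compares men offered pregabalin from the start with men offered it from week 6. The second six weeks are open label, and the outcome is the participant's own judgement of change. If pregabalin works, placebo men who switch should improve and the difference between arms should narrow. An unresolved choice of time point also leaves room to pick one after the results are known.

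**Working it through.** **1. The passages side by side**

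| Section | GRA time point or bearing on it |
|---|---|
| 5.2 | 12 weeks, or withdrawal if earlier |
| 12.1 | 6 weeks for the primary and all secondary endpoint analyses; GRA looked at again at the end of Phase II |
| 12.8 | 6 weeks, or withdrawal if earlier |
| 12.9 | Phase II analyses exploratory only |
| Appendix A | GRA collected at both week 6 and week 12 |

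Section 5.2 cannot hold together with 12.1 and 12.8. Appendix A is compatible with either time and does not decide between them.

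**2. Who has a week-12 GRA**

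Visit 9 belongs to Phase II. Under Section 9.6 and Appendix A, a man who declines Phase II has his last scheduled contact by telephone at week 7 (Visit 6). Under 5.2 he has no endpoint value unless declining is read as withdrawal. If it is read that way, the endpoint mixes assessments at about week 6 or 7 with assessments at week 12.

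**3. The plan's own sample size**

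Inputs from Section 12.2: 40% against 60%, two-sided 0.05, 90% power, 2:1 allocation, 287 before adjustment and 318 after (212/106). These are for the NIH-CPSI responder endpoint; no figure is given for the GRA.

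- Unpooled variance: placebo n = (1.960 + 1.282)² × (0.40×0.60 + 0.60×0.40/2) / 0.20² = 94.6, total 283.7.
- Pooled variance under the null, without continuity correction: 97 placebo, 291 in total.
- Adjustment: 287 × 1.10 = 315.7; 287 / 0.90 = 318.9.

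The stated 287 and 318 are reproduced to within 3%.

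**4. Illustration of the week-12 contrast**

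Assumptions, none of them from the documents for the GRA: response is 60% on drug and 40% on placebo; a share f of the placebo arm takes open-label drug and responds at 60% by week 12; the pregabalin arm stays at 60%.

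- Placebo-arm rate: p_c = 0.40 + 0.20 f. Difference: d = 0.60 − p_c.
- Pooled rate: p̄ = (p_c + 2×0.60)/3.
- SE₀ = √[p̄(1 − p̄)(1/106 + 1/212)].
- SE₁ = √[p_c(1 − p_c)/106 + 0.60×0.40/212].
- Power = Φ[(d − 1.96 SE₀)/SE₁].

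For f = 0.50: p_c = 0.50, d = 0.10, p̄ = 0.5667, SE₀ = 0.0589, SE₁ = 0.0591. Then (0.10 − 0.1155)/0.0591 = −0.263, and power = 0.396.

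| f | Difference (points) | Power at 212/106 |
|---|---|---|
| 0 (as at week 6) | 20 | 92.4% |
| 0.25 | 15 | 71.8% |
| 0.50 | 10 | 39.6% |
| 0.70 | 6 | 17.5% |
| 0.85 | 3 | 7.5% |
| 1 | 0 | no effect left to detect |

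The model is crude. It gives placebo men who decline Phase II a 40% response at week 12, although they have no scheduled GRA then. It holds pregabalin men who have stopped and tapered at 60%. It ignores self-selection into Phase II. It shows direction, not an expected size.

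**The case against.** The strongest reply is that the plan already analyses the GRA at week 6. Section 12.1 says so for all secondary endpoints, 12.6 describes outcomes at the 6-week visits, 12.8 says so for the GRA, and 12.9 confines Phase II to exploratory work. Only one sentence, in 5.2, says 12 weeks, and it specifies no between-arm test. It may describe the Phase II reassessment of the GRA mentioned in 12.1 without labelling it as such; the reporting table in 12.10 also lists a final report at 6 and 12 weeks. This is a fair account of probable intent and limits how serious the point is. It does not remove the conflict, because 5.2 is where the endpoint is defined.

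Three stronger readings are tempting, and the documents support none of them.

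- A reader might infer that the trial plans a confirmatory test of pregabalin against delayed pregabalin and so is likely to miss a real effect. No section plans such a test, no alpha or power is assigned to the GRA, and 12.10 says early closure will generally not rest on secondary endpoints. Being named first in 5.2 does not make the GRA a key secondary.
- A reader might infer that the 6-point cut-off is undermined, since the GRA was its anchor. Section 5.1 shows that the anchoring used a previous trial's data from baseline to 6 weeks. The GRA timing in this trial cannot affect it.
- A reader might infer that 12.8 breaks the plan's rule on withdrawals by using the GRA reported on leaving. The rule in 12.4 ("These participants will be considered treatment failures and included in the denominator") is written for response rates on the primary endpoint. When 12.8 calls the analysis the same as the primary one, it may mean only the exact Mantel-Haenszel test of 12.7. Since 12.7 also mentions counting withdrawals as non-responders, the text is ambiguous but not contradictory.

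The objection that the power figures are hypothetical stands in full.

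**Conclusion.** The definition in 5.2 is wrong as written and conflicts with 12.1, 12.8 and the exploratory status of Phase II in 12.9. Applied literally, it gives a GRA comparison without a placebo control, no scheduled value for men who decline Phase II, and a tendency to shrink a true effect. That tendency assumes that pregabalin works and that some placebo men take up the open-label offer.

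The consequence is limited to one supportive secondary endpoint. The primary endpoint and its sample size are unaffected. The dilution, from 20 points at week 6 down to 0 if every placebo man switches and responds at the drug rate, is illustrative only, because the documents give no GRA response rates and no Phase II uptake. The handling of withdrawals in the GRA analysis needs clarification and is a minor matter.

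**What to change.** In Section 5.2, replace twelve weeks by six weeks (Visit #5) in the GRA definition, so that it agrees with 12.1 and 12.8. Report the week-12 GRA only as an exploratory Phase II summary, and say so in 12.9.

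In Section 12.8, add one sentence stating whether a man who withdraws before week 6 counts as a GRA non-responder, as in the primary analysis, or is classified by the GRA recorded at withdrawal. Either rule can be defended if it is stated in advance.

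The cost is wording only. Section 9.5 and Appendix A already collect the GRA at Visit 5, so no visit, form or sample-size change is needed. The change should be made before treatment codes are released.
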